9. STATISTICAL CONSIDERATIONS

a) Study Endpoints

The primary endpoint is feasibility, measured as percentage of patients continuing TTF therapy until

intracranial tumor progression, discontinuation due to DLT, or 6 months. Death prior to evidence of intracranial failure is treated as a competing risk and the patient is censored at time of death. Death will not be considered as an event and patients who have not had intracranial failure will be censored at the time of death.

Secondary endpoints include:

- Time to intracranial failure, as measured from date of starting NovoTTF-200A to intracranial failure as a first event. Death prior to evidence of intracranial failure is treated as a competing risk and will be censored on the time to intracranial failure curves.
 - Intracranial Failure will be diagnosed based on ONE of the following criteria:
 - New lesion seen on two consecutive axial slices
 - New lesion seen on at least one slice in two separate planes
 - MRI used to diagnose intracranial failure must meet requirements mentioned in inclusion criteria, specifically, the MRI must be a high resolution, isovolumetric T1-weighted post-gadolinium MRI of the brain using a 3T MR scanner. Additional parameters include:
 - FOV: 256 mm x 256 mm
 - Matrix: 256x256
 - Slice thickness: 1 mm
 - Full brain Coverage
 - A lesion is designated “Undetermined” as long as it does not comply with the definition of intracranial failure above. If on a subsequent scan or on an additional imaging modality it is deemed as intracranial failure according to the criteria above, the date of intracranial failure diagnosis will be documented as the first time a new lesion was evident on a scan (i.e., backdated).
- Overall survival, defined from the date of starting NovoTTF-200A to death due to any causes, or censored at the date of last follow-up.
- Rate of intracranial failure at 2, 4, 6, 8, 10, 12 month after starting NovoTTF-200A
- Intracranial failure free survival, defined from the date of starting NovoTTF-200A to the first intracranial failure or death (whichever occurs first) or, otherwise, censored at the last MRI imaging assessment date on which the patient was reported alive without intracranial failure.
- Rate of decline in cognitive function as measured by HVLT-R free recall, delayed recall, and delayed recognition; COWAT; and TMT Parts A and B at 2, 4, 6, 8, 10, 12 months follow-up.
- Time to neurocognitive failure, as measured by cognitive decline on a battery of tests: HVLT-R free recall, delayed recall, and delayed recognition; COWAT; and TMT Parts A and B.
- Neurocognitive failure-free survival, defined from the date of starting NovoTTF-200A to neurocognitive failure (as measured by HVLT-R free recall, delayed recall, and delayed recognition; COWAT; and TMT Parts A and B) or death (whichever occurs first), censored at the last neurocognitive assessment on which the patient was reported alive without neurocognitive failure.
- Quality of Life using the EORTC QLQ C30 with BN20 addendum.
- Toxicity during NovoTTF-200A treatment based on incidence and severity of treatment emergent adverse events as evaluated using the CTCAE version 5.0 (**Appendix D**).

The above battery of neurocognitive instruments has been selected based on accepted standardization and psychometric principles, published normative data relative to routine demographics, relevance to general neurocognitive status, minimal practice effects, and brevity of the overall battery. Additionally, similar variations of this neurocognitive testing battery have been utilized in multiple cooperative group trials including RTOG 0212, RTOG 0214, RTOG 0424, RTOG 0525, RTOG 0933, ACOSOG Z0933,

NCCTG N0574, NCCTG N0577, RTOG 0825, ECOG E3F05, NCCTG N0874/ABTC 09-0, and N107C. Assessments will be conducted every 8 weeks for the first year or until intracranial failure, whichever occurs first. The HVLt-R test has been used and validated in multiple prior phase III trials of patients with brain metastases [9, 21]. HVLt-R incorporates 6 different forms, helping to mitigate practice effects of repeated administrations. Each form includes 12 nouns (targets) with 4 words drawn from 3 semantic categories, which differ across the 6 forms. The test involves memorizing a list of 12 targets for 3 consecutive trials (immediate recall), recalling the 12 targets after a 20-minute delay (delayed recall), and identifying the 12 targets from a list of semantically related or unrelated items (delayed recognition). In COWAT [Johnson SC et al, *Clin Neuropsychol.* 2012; 26(7):1230-41, Johnson DR et al, *Neuro Oncol.* 2012;14(6):808-16], the patient produces as many words as possible in 1 minute for a specific letter and the test assesses language and executive/frontal skills. The test is widely used and is part of the Halstead-Reitan Neuropsychological Battery. Impairment in the understanding of language or the motor expression of language will impair the results in this trial. Since such functions are affected by brain-directed therapies such as WBRT, the test could be sensitive to the experimental treatment effects on those functions. TMT [Bowie CR and Harvery PD, *Nat Protoc.* 2006; 1(5):2277-81] is a measure of visuospatial scanning, attention, sequencing and cognitive processing speed (Part A) and executive function (Part B). Those neurocognitive functions could be affected both by brain metastasis and by therapies directed to the brain, and will therefore be used in the trial. Patients must “connect the dots” either in a numbered sequence or alternating letters and numbers.

b) Sample Size Determination: Because the primary endpoint is feasibility, the proposed sample size is not driven by statistical hypotheses. Rather, we propose the sample size of 25 so that we will have precise enough information for planning the next phase of treatment development. The following table summarizes the point estimate and 95% confidence interval when n=25.

# patients continuing therapy	10	15	18	20
Point estimate	40%	60%	72%	80%
95% confidence interval	23% - 59%	41% - 77%	52% - 86%	61% - 91%

c) Statistical Analysis – Primary Endpoint: Since this is a feasibility study, we will not attempt a strict control of multiplicity in analyses of the primary and secondary endpoints. Proportion of patients continuing TTF will be estimated using Wilson’s method and a one-sided 95% confidence interval will be reported. We will also summarize this measure for those who had PR and CR separately.

d) Statistical Analysis – Secondary Endpoints

Secondary endpoints for statistical testing: Time to intracranial failure with death as a competing risk will be estimated using cumulative incidence function (CIF) and reported with a one-sided 95% confidence interval. Rate of intracranial failure at a given time will be estimated using the CIF. Overall survival will be estimated using the Kaplan-Meier method. Other time-to-events data (with or without competing risks) will be analyzed similarly. Quality of life will be treated as a continuous endpoint; its mean will be estimated and reported with a 95% confidence interval. Toxicity (CTCAE 0-4) will be tabulated.

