1. OVERALL SYNOPSIS OF THE CLINICAL INVESTIGATION

Title:	A Multi-Institutional Pilot Study of Prophylactic Cranial Tumor-Treating Fields for Patients with Extensive-stage Small Cell Lung Cancer
Device:	NovoTTF-200A System (200kHz output frequency)
Study Objectives:	To test the feasibility and compliance of TTF therapy to the brain in patients with extensive-stage small cell lung cancer with no evidence of brain metastasis. Secondary endpoints include overall survival, development of brain metastases, neurocognitive function, and QOL outcomes.
Study Design:	Prospective open label pilot study
Study Hypothesis:	The hypothesis of this study is that NovoTTF-200A will reduce the risk of developing brain metastases for ES-SCLC patients.
Sample Size:	25 patients treated with NovoTTF-200A
Study Population:	Patients with histologically proven small cell lung cancer who have undergone at least four cycles of first-line chemotherapy with a partial or complete response, above 22 years of age, no evidence of intracranial metastasis.
Primary Endpoint:	Feasibility, as measured by tolerability of TTFs (% patients continuing TTF therapy until intracranial tumor progression, discontinuation due to DLT, or 6 months).
Secondary Endpoints:	
 • Time to intracranial failure • Overall survival • Rates of intracranial failure at 2, 4, 6, 8, 10, 12 months after NovoTTF-200A • Intracranial failure free survival • Rate of decline in HVLt-R free recall, delayed recall and delayed recognition, COWAT and TMT Parts A and B at 2, 4, 6, 8, 10, 12 months after NovoTTF-200A • Time to neurocognitive failure • Neurocognitive failure-free survival • Quality of Life using the EORTC QLQ C30 with BN20 addendum • Adverse events, severity and frequency based on CTCAE V5.0
Sponsor:	[name], Vanderbilt University Medical Center

STUDY SCHEMA

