5. OBJECTIVES AND HYPOTHESES OF THE CLINICAL INVESTIGATION

a) Purpose and Objectives

Purpose

To test the feasibility of prophylactic cranial TTF therapy in preventing brain metastases in ES-SCLC patients who have a partial or complete response of extracranial disease after at least 4 cycles of first line chemotherapy.

Primary Objective

To measure the feasibility and compliance of NovoTTF-200A as prophylactic cranial TTF therapy, determined by % of patients continuing TTF therapy until intracranial tumor progression, discontinuation due to DLT, or 6 months.

Secondary Objectives

1. To evaluate time to intracranial failure after NovoTTF-200A.
2. To evaluate overall survival after NovoTTF-200A.
3. To evaluate the rates of intracranial failure at 2, 4, 6, 8, 10, 12 months after NovoTTF-200A.
4. To evaluate intracranial failure free survival after NovoTTF-200A.
5. To evaluate the rate of decline in HVL-R free recall, delayed recall and delayed recognition, COWAT and TMT Parts A and B at 2, 4, 6, 8, 10, 12 months after NovoTTF-200A.
6. To evaluate time to neurocognitive failure after NovoTTF-200A.
7. To evaluate neurocognitive failure-free survival after NovoTTF-200A.
8. To evaluate Quality of Life using the EORTC QLQ C30 with BN20 addendum after NovoTTF-200A.
9. To assess adverse events, severity, and frequency associated with NovoTTF-200A using the CTCAE version 5.0.

b) Hypotheses

The hypothesis of this study is that NovoTTF-200A will reduce the risk of developing brain metastases for ES-SCLC patients.

c) Intended Performance of the Investigational Device

This prospective open label pilot study is designed to study the safety, tolerability and feasibility of NovoTTF-200A to the brain as prophylactic cranial therapy for ES-SCLC patients.

d) Risks and Anticipated Adverse Device Effects That are to be Assessed

See **Section 4** (Risks and Benefits of the Investigational Device and Clinical Investigation).

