6. DESIGN OF THE CLINICAL INVESTIGATION

1. General

a) Description of the Type of Clinical Investigation to be Performed

This is a prospective, single-arm, open-label multicenter pilot study. All patients will undergo TTFs using the NovoTTF-200A System set to an output frequency of 200 kHz. Patients on the study may receive chest irradiation at the discretion of the treating physician. Moreover, should the patient develop progressive extracranial disease, then the patient may receive systemic therapy at the discretion of the treating physician. All oncology therapies will be recorded in the clinical trial record.

NovoTTF-200A will be discontinued in patients who develop intracranial failure while on therapy. All patients who develop intracranial failure may undergo WBRT or best supportive care at the discretion of the treating physician.

All study follow-up procedures should continue according to the study's protocol until death, or until one of the other criteria for removal from the study is met (see **Section 3.C** below).

b) Outcome Measures

Primary Outcome Measure:

Feasibility, as measured by tolerability of TTFs, will be recorded as percentage of patients continuing TTF therapy until intracranial tumor progression, discontinuation due to DLT, or continuation of therapy for at least 6 months.

Secondary Outcome Measures:

1. Time to intracranial failure, as measured from date of starting NovoTTF-200A to intracranial failure as a first event. Death prior to evidence of intracranial failure is treated as a competing risk and will be censored on the time to intracranial failure curves.
2. Overall survival, defined from the date of starting NovoTTF-200A to death, or censored at the date of last follow-up.
3. Rate of intracranial failure at 2, 4, 6, 8, 10, 12 months after starting NovoTTF-200A
4. Intracranial failure free survival, defined from the date of starting NovoTTF-200A to the first intracranial failure or death (whichever occurs first) or, otherwise, censored at the last MRI imaging assessment date on which the patient was reported alive without intracranial failure.
5. Rate of decline in cognitive function as measured by HVLT-R free recall, delayed recall, and delayed recognition; COWAT; and TMT Parts A and B at 2, 4, 6, 8, 10, 12 months follow-up.
6. Time to neurocognitive failure, as measured by cognitive decline on a battery of tests: HVLT-R free recall, delayed recall, and delayed recognition; COWAT; and TMT Parts A and B.

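### Section 9(a) censors deaths within the primary endpoint, but Section 9(c) analyses that endpoint as a Wilson proportion, which cannot use a censored patient; the coding of deaths on the device is left open

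*Combined protocol and SAP*

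**What the plan says.** The primary endpoint is a percentage. Section 5(a) words it as "determined by % of patients continuing TTF therapy until intracranial tumor progression, discontinuation due to DLT, or 6 months", and the synopsis, Section 6.1(b) and Section 9(a) list the same three endings. Death is not among them.

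Section 9(a) adds two sentences to the primary-endpoint paragraph, before the secondary endpoints begin: "Death prior to evidence of intracranial failure is treated as a competing risk and the patient is censored at time of death" and "Death will not be considered as an event and patients who have not had intracranial failure will be censored at the time of death".

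Section 9(c) gives the analysis: "Proportion of patients continuing TTF will be estimated using" Wilson's method, with a one-sided 95% interval. Section 9(b) justifies the sample size by the precision of that proportion: "The following table summarizes the point estimate and 95% confidence interval when n=25".

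The only competing-risk estimator is in Section 9(d), for secondary endpoints: "Time to intracranial failure with death as a competing risk will be estimated using cumulative incidence function (CIF". Separately, the treatment-duration item in Section 6.6(a) lists death, with intracranial failure and unacceptable side effects, among the points up to which treatment continues.

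**The concern.** A Wilson interval takes x successes out of n patients. Censoring belongs to time-to-event methods and has no counterpart in that calculation. The instruction in 9(a) therefore cannot be carried out with the analysis in 9(c), and someone has to decide what a censored death becomes.

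Three codings are open for a patient who dies on the device before 6 months:

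- **Non-continuer**, because the patient reached none of the three listed endings.
- **Excluded**, which is how censoring might be imitated in a proportion. It takes the denominator below the 25 used in 9(b).
- **Continuer**, because 9(a) says death is not an event and Section 6.6(a) names death as a planned end of treatment.

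The study is open-label with a single arm, so without a written rule the coding could be chosen after the deaths are known. It affects the study's one primary estimate, which Section 9(b) says is meant to inform planning of the next phase.

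**Working it through.** **Inputs from the documents.** n = 25 and the table of intervals (9(b)). Wilson's method with a one-sided 95% interval (9(c)). Anticipated rate of at least 75% tolerating 6 months or more (3(e)). Median overall survival of 5.4 and 6.7 months in one cited trial and 10.1 and 15.1 months in the other (3(a)).

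**Assumed inputs.** d = deaths on the device before 6 months without a listed ending; s = other early stops outside the listed endings. The documents give neither.

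**Step 1: reproduce the plan's table.** With p = x/n, the Wilson limits are

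[p + z²/(2n) ± z·√(p(1−p)/n + z²/(4n²))] / (1 + z²/n).

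Two-sided 95%, z = 1.960, n = 25:

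| x | Computed | Printed |
|---|---|---|
| 10 | 23.4–59.3% | 23–59% |
| 15 | 40.7–76.6% | 41–77% |
| 18 | 52.4–85.7% | 52–86% |
| 20 | 60.9–91.1% | 61–91% |

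All four agree. An exact (Clopper-Pearson) interval for 10/25 would be 21.1–61.3%, which does not. The planned calculation is thus a binomial over a fixed 25, with every patient classified.

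**Step 2: effect of one death.** Let c = 25 − d − s be the patients who meet the definition. The three codings give c/25, c/(25 − d) and (c + d)/25. The gap between the extremes is d/25, or 4 percentage points per death, whatever s is.

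**Step 3: illustration, d = 3 and s = 3 (assumed), so c = 19.** One-sided 95% lower bounds use z = 1.645. For 19/25, the centre is (0.76 + 0.0541)/1.1082 = 0.7346 and the half-width is 1.645 × 0.0915/1.1082 = 0.1359, so the bound is 0.599.

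| Coding of the 3 deaths | Estimate | Lower bound |
|---|---|---|
| Non-continuer | 19/25 = 76% | 60% |
| Excluded | 19/22 = 86% | 70% |
| Continuer | 22/25 = 88% | 73% |

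**Step 4: range over s, with d = 3.**

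| s | Non-continuer | Excluded | Continuer |
|---|---|---|---|
| 0 | 22/25 = 88% | 22/22 = 100% | 25/25 = 100% |
| 6 | 16/25 = 64% | 16/22 = 73% | 19/25 = 76% |

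**Step 5: how many deaths might there be?** Under an assumed exponential curve, the proportion dead by 6 months is 1 − 0.5^(6/median). Medians of 5.4, 6.7, 10.1 and 15.1 months give 54%, 46%, 34% and 24%, or about 6 to 13 of 25. This is deaths from any cause. It is an upper guide to d, because it includes deaths after intracranial failure and after stopping the device. Survival in this trial may also differ from that in the cited trials.

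**The case against.** The strongest reply is that the two sentences are misplaced. Both are framed around intracranial failure, and the first nearly repeats the definition of time to intracranial failure just below it. The synopsis and Sections 5(a) and 6.1(b) define the primary endpoint without them. On a charitable reading, death not being an event means only that it does not count as intracranial progression, and then nothing opposes 9(c). This is probably how the text arose. But the sentences stand in the primary-endpoint paragraph, and ignoring them still leaves no stated coding for a death on the device.

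It is also fair to say that the analysis is descriptive and that deaths will be visible through overall survival. That limits the harm but does not supply a rule.

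Three stronger readings are tempting, and the documents do not support them:

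- *That the plan states a default of non-continuer.* It states none. That coding is an inference from the absence of death among the listed endings, and Section 6.6(a) gives some support to the opposite one. The n = 25 table weighs only against exclusion, since coding deaths as continuers also keeps 25 in the denominator.
- *That the censoring also reaches patients who stop the device early and die later without intracranial failure.* The words carry no on-device restriction, but such a patient's outcome for continuing therapy has already been observed, and a later death cannot undo it.
- *That the coding could decide whether the study succeeds.* Section 3(e) anticipates at least 75% and makes consideration of a phase 2 study depend on safety and tolerability, but no section sets a test or threshold.

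**Conclusion.** The point stands and should be fixed. A stated rule for deaths in 9(a) cannot be applied in the analysis stated in 9(c), and the documents do not choose among the three codings that remain. That incompatibility rests on the text alone, and confidence in it is high.

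The shift of 4 percentage points per affected death between the extreme codings is exact for n = 25. The spread of 76%, 86% and 88% depends on the assumed 3 deaths and 3 other stops. Set beside the anticipated 75%, it runs from about that rate to well above it, by coding alone. The number of affected deaths cannot be derived from the documents. The cited survival figures make some deaths within 6 months plausible, but give only an upper guide. What changes is the reported estimate and its lower bound, not a formal decision.

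**What to change.** In Section 9(a), delete the two censoring sentences from the primary-endpoint paragraph and keep the handling of death under time to intracranial failure.

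In Section 9(c), state:

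1. The Wilson denominator is all patients who started the device, with no exclusion for death.
2. A patient still on the device who dies before 6 months without one of the listed endings is a non-continuer. This follows the endpoint definition as written.
3. The same proportion, with those deaths counted as continuers, is reported as a pre-specified sensitivity analysis with its one-sided Wilson bound.

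The cost is wording in two subsections and one extra proportion. No new data are needed. The reported primary figure may be less favourable than under the other codings.

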However, the role of PCI in ES-SCLC patients who have a good response to initial systemic therapy remains unclear. To date, there have been two randomized multicenter trials which evaluated PCI in ES-SCLC. An EORTC phase III trial by Slotman et al., randomized ES-SCLC patients with a response to chemotherapy to either PCI or observation. The primary end point for this study was symptomatic brain metastases. Of note, intracranial screening by MRI was not utilized prior to PCI. When compared to observation, PCI was associated with a lower risk of symptomatic brain metastases (hazard ratio [HR], 0.27; 95% confidence interval [CI], 0.16 to 0.44; $P < 0.001$), higher median disease-free survival (14.7 weeks vs 12.0 weeks), and higher median overall survival (6.7 months vs 5.4 months). The cumulative risk of brain metastases within 1 year was 14.6% in the irradiation group (95% CI, 8.3 to 20.9) vs 40.4% in the control group (95% CI, 32.1 to 48.6), and the 1-year survival rate was 27.1% (95% CI, 19.4 to 35.5) in the irradiation group vs 13.3% (95% CI, 8.1 to 19.9) in the control group [6].

Another phase III trial was performed in Japan, in which ES-SCLC patients with some response to initial chemotherapy were randomized to either PCI or observation. Unlike the EORTC trial, this trial required MRI screening prior to randomization. Preliminary interim analysis, presented at the American Society of Clinical Oncology annual meeting in 2014, demonstrated a trend towards worse overall survival with PCI (10.1 months vs 15.1 months, HR 1.38; 95% CI, 0.95 to 2.01; stratified log-rank test, $p = 0.091$). Compared to observation, PCI significantly reduced the risk of brain metastases (32.4% vs 58.0% at 12 months; Gray's test, $p < 0.001$) and had comparable PFS (median, 2.2 vs 2.4 months; HR 1.12; 95% CI, 0.82 to 1.54) [7].

Both the EORTC and Japanese trials confirm the impact of PCI on reducing the incidence of brain metastases in ES-SCLC patients. However, these trials provide conflicting data on whether PCI provides a survival benefit. Moreover, PCI adversely affects short term quality of life with side effects such as fatigue and hair loss [6]. In addition, there is concern for long-term radiation-induced neurological morbidity [8], [9]. As treatment for ES-SCLC becomes more successful, efforts to minimize neurotoxicity from PCI will be of paramount importance.

b) Tumor Treating Fields (TTFields) Overview

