7. Neurocognitive failure-free survival, defined from the date of starting NovoTTF-200A to neurocognitive failure (as measured by HVLT-R free recall, delayed recall, and delayed recognition; COWAT; and TMT Parts A and B) or death (whichever occurs first), censored at the last neurocognitive assessment on which the patient was reported alive without neurocognitive failure.
8. Quality of Life using the EORTC QLQ C30 with BN20 addendum.
9. Toxicity during NovoTTF-200A treatment based on incidence and severity of treatment emergent adverse events as evaluated using the CTCAE version 5.0

c) Methods and Timing for Assessing, Recording, and Analyzing Variables.

See under Statistical Considerations (**Section 9**).

2. Investigational Device(s) and Comparator(s)

The investigational device and comparators are described as part of the study treatments below.

3. Subjects

Inclusion Criteria:

1. 22 years of age and older
2. Life expectancy of > 3 months
3. Histologically proven ES-SCLC (any T any N and any M stage) within 6 months prior to start of study treatment with the NovoTTF-200A, with a partial or complete response to at least four cycles of first-line chemotherapy
4. Karnofsky performance status (KPS) > 70 (see **Appendix A**)
5. Adequate hematological, hepatic and renal function, defined as: Neutrophil count > $1.5 \times 10^9/L$ and platelet count > $100 \times 10^9/L$; bilirubin < $1.5 \times ULN$; AST and/or ALT < $2.5 \times ULN$ or < $5 \times ULN$ if patient has documented liver metastases; and serum creatinine < $1.5 \times ULN$.

Exclusion Criteria:

1. Evidence of brain metastases on MRI of brain with and without contrast
2. History of other prior malignancy within the past 5 years except for superficial skin cancers
3. No severe comorbidities:
 - a. History of significant cardiovascular disease unless the disease is well controlled.

Significant cardiac disease includes second/third degree heart block; significant ischemic heart disease; poorly controlled hypertension; congestive heart failure of the New York Heart Association (NYHA) Class II or worse (slight limitation of physical activity; comfortable at rest, but ordinary activity results in fatigue, palpitation or dyspnea).

- b. History of arrhythmia that is symptomatic or requires treatment. Patients with atrial fibrillation or flutter controlled by medication are not excluded from participation in the trial.

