7. PATIENT EVALUATIONS AND FOLLOW UP PLAN

A table of the study procedure calendar for this study is provided in **Appendix C**.

a) Pre-treatment Evaluation (Baseline)

The following will be performed within 21 days prior to registration (start of study treatment with the NovoTTF-200A System):

1. Verify informed consent is signed
2. A high resolution, isovolumetric T1-weighted post-gadolinium MRI of the brain using a 3T MR scanner. **Treatment with the NovoTTF-200A System is to begin no later than 21 days after the baseline MRI.** Additional parameters include:
 - a) FOV: 256 mm x 256 mm

- b) Matrix: 256x256
- c) Slice thickness: 1 mm
- d) Full brain coverage

The same slice thickness and contrast material type & dose should be maintained throughout the entire study. The NovoTTF-200A System and all components including the transducer arrays must be removed and cannot be brought into the MR environment.

- 3. Medical history
- 4. Concomitant medications
- 5. Karnofsky Performance Status (KPS) score recording
- 6. Physical examination and vital signs
- 7. Neurological examination
- 8. Neurocognitive testing: Hopkins Verbal Learning Test (HVLT-R) for free recall, delayed recall and delayed recognition, Controlled Oral Word Association Test (COWAT); and Trail Making Tests (TMT) Parts A and B
- 9. Quality of Life questionnaire (EORTC QLQ C30 with BN20 addendum)
- 10. Serum Pregnancy test (if applicable) within 14 days
- 11. Complete blood count including differential
- 12. Serum chemistry panel, including:
 - 1. BUN, Creatinine
 - 2. Sodium, Potassium
 - 3. ALT, AST, Bilirubin
- 13. Coagulation tests (PT, PTT)

b) Follow-up until Intracranial Failure

Once every 8 weeks until intracranial failure the following examinations will be performed:

- 1. Physical examination and vital signs
- 2. KPS score recording
- 3. Neurological examination
- 4. Complete blood count including differential
- 5. Serum chemistry panel, including:
 - 1. BUN, Creatinine
 - 2. Sodium, Potassium
 - 3. ALT, AST, Bilirubin
- 6. Coagulation tests (PT, PTT) as clinically indicated
- 7. Adverse event collection and recording
- 8. Concomitant medication recording
- 9. A high resolution, isovolumetric T1-weighted post-gadolinium MRI of the brain using a 3T MR scanner. Additional parameters include:
 - a) FOV: 256 mm x 256 mm
 - b) Matrix: 256x256
 - c) Slice thickness: 1 mm
 - d) Full brain coverage

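### Time to intracranial failure: the endpoint text says deaths are censored, but section 9(d) estimates a cumulative incidence function with death as a competing risk

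*Combined protocol and SAP*

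**What the plan says.** The definition of time to intracranial failure is the same in section 6.1(b), secondary outcome 1, and in section 9(a): "Death prior to evidence of intracranial failure is treated as a competing risk and will be censored on the time to intracranial failure curves".

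The primary-endpoint paragraph at the top of section 9(a) also calls death a competing risk with censoring at death, and then adds: "Death will not be considered as an event and patients who have not had intracranial failure will be censored at the time of death".

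Section 9(d), the analysis text, says "Time to intracranial failure with death as a competing risk will be estimated using cumulative incidence function (CIF" and "Rate of intracranial failure at a given time will be estimated using the CIF". It names Kaplan-Meier only for overall survival. It does not say how a death is to be coded in the dataset.

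The definition of time to intracranial failure gives no censoring date for a patient who is alive without failure. Intracranial failure-free survival does have one: such patients are "censored at the last MRI imaging assessment date on which the patient was reported alive without intracranial failure".

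**The concern.** In a CIF, a death before intracranial failure is a second type of event. A censored observation is not an event. One death cannot be coded both ways in the same curve. Section 9(d) names the estimator, but the only words on coding are in the endpoint definitions, and they say that deaths are censored. The primary-endpoint paragraph says so again, more explicitly.

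A programmer who builds the event variable from the definitions would give the CIF routine only one event type. It would then return 1-KM, which describes failure as if nobody died first. If both the curve and the landmark rates were coded this way, both would be overstated. If only the curve were, it would disagree with the 2 to 12 month rates printed beside it.

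This endpoint bears directly on the stated hypothesis, that the device reduces the risk of brain metastases. With no control arm, readers will compare it with outside rates such as those in section 3(a). The Japanese rates there are reported with Gray's test, which belongs to the CIF framework, so a 1-KM figure would not be like for like.

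**Working it through.** The plan gives no expected figure for this endpoint, so there is none to reproduce. The check covers the technical statement first, then the possible size.

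**1. Does censoring deaths turn the CIF into 1-KM?** The CIF adds, at each failure time, (share still event-free just before) × (failures ÷ number at risk). The event-free share falls at every failure and every death. If deaths are recoded as censored, that share falls only at failures and becomes the Kaplan-Meier curve for failure alone, so the sum equals 1-KM. A 25-patient test dataset confirmed this. The Kaplan-Meier weight is never smaller than the event-free share, so 1-KM is never below the CIF.

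**2. Inputs (section 3(a), EORTC trial).** One-year risk of brain metastases F: 40.4% control, 14.6% PCI, read here as a CIF. One-year overall survival: 13.3% control, 27.1% PCI. The share alive without failure, EF, is not given. It is set at overall survival, which is its ceiling because some survivors will have had failure.

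**3. Constant ratio of failure to death hazards.** 1-KM = 1 − EF^(F/(1−EF)).

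- Control: 1 − 0.133^(0.404/0.867) = 0.609; excess 20.5 points.
- PCI: 1 − 0.271^(0.146/0.729) = 0.230; excess 8.4 points.

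**4. Timing.** Let failures be uniform over the first W months and deaths without failure, d = 1 − EF − F, uniform over 12 months. With a = F/W and b = d/12, 1-KM = 1 − (1 − (a+b)W)^(a/(a+b)). For control with W = 6: a = 0.0673, b = 0.463/12 = 0.0386, 1-KM = 0.474, excess 7.0 points.

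| 12-month excess, points | W=12 | W=9 | W=6 | W=3 |
|---|---|---|---|---|
| EORTC control | 20.5 | 12.3 | 7.0 | 3.1 |
| EORTC PCI | 8.4 | 5.1 | 2.9 | 1.3 |

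If every failure precedes every death, the excess is zero.

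**5. Why 20.5 is not an upper bound.** A lower EF means more deaths without failure. Keeping F = 0.404 and the constant ratio, an assumed EF of 10% gives 1 − 0.10^(0.404/0.90) = 0.644, an excess of 24.0 points; an assumed 5% gives 1 − 0.05^(0.404/0.95) = 0.720, or 31.6. Timing is not at its extreme either: at EF = 13.3%, if all deaths came first, 1-KM would be 0.404/(0.404 + 0.133) = 0.752, or 34.8 points.

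**6. MRI-screened Japanese arms (section 3(a); EF assumed, not in the documents).** With F = 58.0% and EF from 40% to 25%, the excess is 0.8 to 7.8 points under a constant ratio and 0.4 to 3.5 with W = 6. With F = 32.4% and EF from 60% to 25%, it is 1.5 to 12.7 and 0.7 to 4.8.

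**7. At n = 25.** Take 10 failures, 12 deaths without failure and 3 patients event-free. The CIF is 10/25 = 40%. 1-KM is 40% if all failures come first, averages about 61% in random order (50,000 permutations), and is 10/13 = 77% if all deaths come first. For scale, the two-sided 95% Wilson interval for 10/25 in section 9(b) is 23% to 59%.

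**The case against.** The strongest reply is that the plan already gets this right. Section 9(d) is the operative analysis text, it names the CIF for both the curve and the rates, and the criticised sentence itself begins by calling death a competing risk. In a CIF calculation a death does leave the risk set for the failure hazard, just as a censored patient does, so the wording may be loose shorthand. A careful statistician would probably code it correctly. All of this stands, and it sets the limits of the point.

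A reader might infer that the sponsor plans a 1-KM analysis. The documents do not support that: Kaplan-Meier is named only for overall survival. Censoring deaths would suit a cause-specific hazard analysis, but none is planned, so that does not explain the wording.

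A reader might also infer that reported failure will be about 20 points too high. That is not supported either. The EORTC endpoint was symptomatic metastases, and the protocol notes: "Of note, intracranial screening by MRI was not utilized prior to PCI". This trial excludes "Evidence of brain metastases on MRI of brain with and without contrast" and schedules MRI on the rule "Once every 8 weeks until intracranial failure the following examinations will be performed". Both the level and the timing of failures may differ here, and the error arises only if the censoring words are followed over 9(d).

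Finally, the primary-endpoint sentences might be read as altering the primary result. Section 9(c) analyses that endpoint as a simple proportion by Wilson's method, in which nothing is censored. How deaths count in that proportion is a separate question.

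What does not fall away is that the sentence states a coding rule, that the rule gives the wrong curve if followed, and that section 9(a) repeats it.

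**Conclusion.** The conflict is real and should be corrected. It is one of event coding, not of the named estimator. Following the censoring wording would replace the CIF with 1-KM and could only overstate intracranial failure.

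The size is illustrative: from zero to about 20 points at 12 months with EORTC control inputs over the failure timings tabulated, and not bounded at 20. It depends on reading the cited 40.4% as a CIF, on setting the event-free share at the 13.3% survival rate, and on the assumed timing of failures relative to deaths.

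The effect is confined to secondary endpoints, namely time to intracranial failure and the 2 to 12 month rates, in a 25-patient single-arm pilot. Intracranial failure-free survival counts death as an event and is untouched. The sample size and the primary proportion do not change. Confidence is high that the wording conflicts; no claim is made that results will in fact be affected.

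**What to change.** 1. In sections 6.1(b) and 9(a), replace the final clause of the time-to-intracranial-failure sentence, the one that censors deaths, with: *and is coded as a competing event, not a censored observation, in the CIF of section 9(d), for both the curve and the 2-12 month rates; only patients alive without intracranial failure are censored, at their last MRI assessment.* The last-MRI date fills the gap for event-free patients with the rule the plan already uses for intracranial failure-free survival.

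2. In the same edit, remove the two death-censoring sentences from the primary-endpoint paragraph of 9(a), or state that they do not govern the intracranial-failure CIF. Without this, section 9(a) would still carry the conflicting instruction a few lines above the corrected one.

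The cost is one clause in two places and two sentences in a third. It needs no new data, no extra analysis, and no change to the sample size or to the primary analysis in 9(c).
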